#### 14.6.3.3. Time to Rescue

Time to Stopping Study Treatment Due to Meeting Rescue Criteria
Meeting Rescue Evaluation Criteria and Rescue Criteria

 
Subjects meeting evaluation criteria for rescue are identified from the Anemia Intervention and Rescue eCRF. Subjects with a record on this form are considered to have met evaluation criteria for rescue. It is possible that a subject could be evaluated for rescue more than once, and in that case a subject would have multiple records on this form.
 
Subjects unable to be evaluated for rescue are subjects who met evaluation criteria for rescue, but were unable to be assessed at the 4 week check (e.g., subjects who died, permanently discontinued study treatment or withdrew from the study before the 4 week check). The outcome of initial intervention eCRF field on the Anemia Intervention and Rescue eCRF will be blank for these subjects.
 

Time to Stopping Study Treatment Due to Meeting Rescue Criteria

 
Subjects meeting rescue are identified by the response “If met rescue criteria, check all that apply” to the outcome of initial intervention question on the Anemia Intervention and Rescue eCRF.
 

Event Date

 
Treatment stop date when the primary reason and subreason for study treatment stop are: 
 
Primary reason: Subject reached protocol-defined stopping criteria
 
Subreason: Rescue
 
 
 

General Definitions

 
Time to event (days) = date of event – randomization date +1
 
Censored time (days) = censoring date – randomization date + 1
 
Rescue person years = (cumulative total time to stopping study treatment for subjects who stopped study treatment due to meeting rescue criteria + cumulative total of censoring time for subjects who did not stop study treatment due to meeting rescue criteria) / 365.25
 
Rescue incidence rate (per 100 person years) = (100 * number of subjects who stopped study treatment due to meeting rescue criteria) / rescue person years
 
Rescue absolute rate difference (per 100 person years) = daprodustat rescue incidence rate (per 100 person years) – rhEPO rescue incidence rate (per 100 person years)
 

Time Period for Treatment Discontinuation

The period for treatment discontinuation begins at randomization. The end of this time period is defined as follows:
 
 
For subjects who did not take study treatment, use the date of randomization
 
For subjects whose treatment stop date is missing and who took study treatment, use study conclusion date
 
For subjects either continuing on study past treatment stop date or completing/withdrawing on the same day as treatment stop date, use treatment stop date
 
 
Any events that occurred before the start of this time period are considered to be prior to the time period for treatment discontinuation, and any endpoints that occurred after the end of this time period are considered to be post the time period for treatment discontinuation.

#### 14.6.3.4. RBC and Whole Blood Transfusion Endpoints

Number of RBC and Whole Blood Transfusions

 
The number of transfusions associated with each RBC and Whole Blood Transfusion record is determined by the frequency, start date, end date and number of units, as described below
 
Only on-treatment transfusions are included. “End date” below refers to the end date defined for the transfusion, or the end of the on-treatment period, if sooner (see Section 14.4.1.1).
 
For records with a frequency of “Once only” or “Continuous infusion”, each record is considered to be a single transfusion (regardless of start and end dates or number of units)
 
For records with a frequency of “Once daily”, the number of transfusions will equal the duration (end date – start date +1)
 

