7.9. Rescue Therapy

A rescue algorithm is provided to minimize participants having an inadequate response to the treatment for their anemia for an extended period of time and to enable consistency in the application of rescue therapy across the study. Details are provided in [Table 8](#).

This rescue algorithm **does not** apply to participants with a low Hgb as a result of an acute or subacute event with an identifiable cause (e.g., GI bleed, blood loss due to surgery or from their vascular access). In these cases, treatment should be directed to the specific cause and study treatment will be continued. If a participant is transfused as part of the treatment, then study treatment will be maintained at the current dose (unless Hgb is ≥ 12 g/dL which requires a dose hold).

Table 8 Rescue Algorithm for Anemia Management

Evaluate Participant for Rescue if:	

 HemoCue Hgb remains <9 g/dL (at a scheduled study visit, Week 4 onwards) despite three ¹ consecutive dose increases above the starting or post-rescue ² dose (where HemoCue Hgb is <9 g/dL prior to each dose increase), or HemoCue Hgb is <7.5 g/dL ³ despite a dose increase at the prior study visit ⁴. 	
Step 1: Initial Intervention	
The following actions will be taken for the initial intervention:
 
 Continue with study treatment (increase dose if HemoCue Hgb <7.5 g/dL; otherwise maintain current dose) A single course of IV iron up to 1000 mg, in addition to following the iron management criteria (Section 7.8.1), if clinically indicated. Transfusion of up to two units of packed red blood cells (PRBC), if clinically indicated. 
At the next study visit, in 4 ± 1 weeks after the initial intervention, recheck HemoCue Hgb as described below in Step 2 (Rescue). Earlier checks of HemoCue Hgb may be obtained to advise further intervention as clinically indicated.

Step 2: Rescue	
 Check HemoCue Hgb 4 ± 1 weeks after the initial intervention Study treatment should be permanently discontinued and the participant should be rescued according to local clinical practice: 
 If HemoCue Hgb remains <9 g/dL, despite initial intervention, based on the average of two HemoCue Hgb values ³, or If more than two units of PRBC were needed for transfusion (and was not related to acute bleeding). 
The participant will remain in the study, and follow the visit schedule in SoA, Table 2.

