## CONFIDENTIAL

204837

Objectives	Endpoints
	
 
• Number (%) of participants with a >1 g/dL increase in Hgb within any 2-week period (assessed at Week 2 through Week 8), or with a >2 g/dL increase in Hgb within any 4-week period up to Week 52
 
• Number (%) of participants with a >1 g/dL decrease in Hgb within any 2-week period (assessed at Week 2 through Week 8), or with a >2 g/dL decrease in Hgb within any 4-week period up to Week 52
 
• N (%) of participants with a Hgb value <math>\geq 12</math> g/dL during the EP
 
• Number of times Hgb <math>\geq 12</math> g/dL during the EP
 
• % of time Hgb <math>\geq 12</math> g/dL during the EP
 

 
• To compare the effect of daprodustat administered three-times weekly to epoetin alfa on measures of iron parameters
 
	
 
• Observed and change from baseline in hepcidin, ferritin, transferrin saturation (TSAT), total iron, total iron binding capacity (TIBC) across all visits
 
• Average quarterly ferritin
 
• Average quarterly TSAT
 
• Average quarterly IV iron dose/participant
 
• N (%) of participants who met iron management criteria
 
• N (%) of participants who reduced IV iron supplementation relative to baseline [defined as total iron (mg) over 4 weeks prior to randomization] during EP [defined as average monthly IV iron dose (mg) over Weeks 28 to 52]
 

 
• To compare the effect of daprodustat administered three-times weekly to epoetin alfa on the need for red blood cell (RBC) and whole blood transfusions
 
	
 
• Number (%) of participants who receive at least one RBC or whole blood transfusion by Week 52
 
• Number of RBC and whole blood transfusions per 100 patient years
 
• Number of RBC and whole blood units per 100 patient years
 

 
• Characterize the pharmacodynamic (PD) effect of daprodustat administered three-times weekly on EPO, vascular endothelial growth factor (VEGF) and RBC
 
	
 
• Maximum observed change from baseline in EPO
 
• Maximum observed % change from baseline in VEGF
 
• Change from baseline in hematocrit, RBC count, and reticulocyte count
 

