#### 14.4.1.1. Study Phases for Hgb, Iron Parameters, IV Iron Dose Endpoints, Iron Use Summaries, Transfusion and PRO Data

Study Phase	Definition
Pre-Treatment	Date $\leq$ Study Treatment Start Date
On-Treatment	Study Treatment Start Date < Date $\leq$ Study Treatment Stop Date + 1 day
Post-Treatment	Date > Study Treatment Stop Date + 1 day
Post-Randomization	Randomization Date < Date

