
Time Period for On-Treatment Transfusions
 
The period for capturing on-treatment transfusions begins on the treatment start date. The end of this time period is defined as follows:
 
 
• For subjects whose treatment stop date is missing and who took study treatment, use date of study withdrawal/completion
 
• For subjects continuing on study past the treatment stop date, use (treatment stop date) For subjects whose study withdrawal/completion date is on or before (treatment stop date), use date of study withdrawal/completion
 

Model Specification
 
 
• Analysis of time to first RBC or whole blood transfusion will be performed using a Cox proportional hazards model adjusted for treatment and region.
 
• Analysis will include only transfusion occurring during the on-treatment period
 

Model Results Presentation
 
 
• The hazard ratio, two-sided 95% CI, and one-sided p-value for the superiority test will be presented for the comparison of daprodustat vs. rhEPO using the Cox Proportional Hazards model.
 
• Number and percentage of subjects who received at least one on-treatment RBC or whole blood transfusion and the number and percentage of censored subjects will be provided by treatment group. The incidence rate per 100 PY (95% CI) within each treatment group and the absolute rate difference per 100 PY (95% CI) will be displayed with the results of the Cox proportional hazards regression model. For within-group rates, the two-sided 95% CI will be obtained using an exact Poisson method. For difference in rates between treatments, the two-sided 95% CI will be constructed with a Normal approximation using Wald's method [Liu, 2006].
 
• A Kaplan-Meier plot will be produced showing the survival function for time to first RBC or whole blood transfusion.
 

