**CONFIDENTIAL**

204837

No.	Population	IDSL / Example Shell	Title	Programming Notes	Deliverable [Priority]
2.058	All Randomized (ITT)	EFF_T26	Summary of Subjects who Reduced On-treatment Monthly IV Iron During the Evaluation Period Relative to Baseline	Subjects who discontinued study treatment before EP will be excluded	SAC
2.059	All Randomized (ITT)	EFF_T27a	Summary of On-treatment RBC or Whole Blood Transfusions During the Evaluation Period and by Week 52		SAC
2.060	All Randomized (ITT)	EFF_T27a	Summary of On-treatment RBC or Whole Blood Transfusions During the Evaluation Period and by Week 52 and by Hyporesponder Status		SAC
2.061	All Randomized (ITT)	EFF_T19	Summary of Analysis of Time to First Occurrence of On-Treatment RBC or Whole Blood Transfusion		SAC
2.062	All Randomized (ITT)	EFF_T29	Summary of Assigned Dose by Visit		SAC
2.063	All Randomized (ITT)	EFF_T30	Summary of Categories of Assigned Dose by Visit for Daprodustat		SAC
2.064	All Randomized (ITT)	EFF_T31	Summary of Categories of Assigned Dose by Visit for rhEPO		SAC
2.065	All Randomized (ITT)	EFF_T33	Summary of Subjects with Dose Adjustments		SAC
2.066	All Randomized (ITT)	EFF_T33.1	Summary of Subjects with Dose Adjustments by Day 1 HemoCue Hemoglobin Category		SAC

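### The count of participants transfused by Week 52 stops at the end of study treatment, so a first transfusion given after stopping is shown as no transfusion

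*SAP*

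**What the plan says.** The objective is to compare the need for red cell and whole blood transfusion. SAP 2.2 words the first endpoint as "Number (%) of participants who receive at least one RBC or whole blood transfusion by Week 52", matching Protocol section 4. Neither wording limits it to time on treatment.

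The derivation does. SAP 14.6.3.4 says "Only on-treatment transfusions are included". Transfusion events, units, patient-year rates and time to first transfusion are restricted in the same way. The main table (2.059, SAP 14.10.6) is titled "Summary of On-treatment RBC or Whole Blood Transfusions During the Evaluation Period and by Week 52" and uses the All Randomized population.

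The end of the window differs between places:
- SAP 14.4.1.1, which governs transfusion data, runs to treatment stop date + 1 day.
- For time to first transfusion, SAP 14.6.3.4 ends at the stop date: "For subjects continuing on study past the treatment stop date, use (treatment stop date".
- The title of Figure 2.035 (SAP 14.10.7) names the on-treatment cardiovascular period, which SAP 14.4.1.2 runs to the last non-zero dose + 28 days.

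Protocol Table 8 sets two rescue steps. In Step 1 study treatment continues, and one permitted action is "Transfusion of up to two units of packed red blood cells (PRBC), if clinically indicated". In Step 2, "Study treatment should be permanently discontinued and the participant should be rescued according to local clinical practice". Needing more than two units, apart from acute bleeding, is itself a Step 2 trigger.

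Protocol Table 2 collects transfusions after permanent discontinuation, at visits to Week 52.

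**The concern.** The percentage has all randomized participants as its denominator and Week 52 in its title, but its event window closes when treatment stops. A participant who stops at, say, Week 20 without a transfusion and receives one at Week 24 is counted among those not transfused by Week 52.

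Time to first transfusion has a related weakness. It is censored when study treatment stops. A Step 2 stop for hemoglobin that stays below 9 g/dL is made for a reason closely tied to the need for transfusion, so the censoring is likely to be informative. The model still yields a hazard ratio and a one-sided superiority p-value.

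The primary analysis (SAP 7.1.4) keeps hemoglobin values regardless of discontinuation, rescue or transfusion. Hemoglobin supported by a post-stop transfusion can therefore enter the primary result while that transfusion appears in no specified transfusion table or model. A reader interpreting the hemoglobin comparison would want that count.

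**Working it through.** The plan has no figure to reproduce here. The check has two parts.

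**1. Which transfusions are counted.** Let S be the treatment stop date. The counts and rates use SAP 14.4.1.1; the time-to-first window uses SAP 14.6.3.4.

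| Transfusion date | Counts and rates (to S + 1) | Time to first (to S) |
|---|---|---|
| Rescue Step 1, on treatment | counted | counted |
| More than two units, given before the stop | counted | counted |
| Day S | counted | counted |
| Day S + 1 | counted | outside |
| Day S + 2 and later | not counted | outside |

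If the Figure 2.035 title were followed, and the last non-zero dose fell on day S, that plot would run to S + 28 and include some post-stop transfusions that the matching model (Table 2.061) leaves out.

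For the percentage and the time-to-first model, only the first transfusion matters. Anyone transfused in Step 1 is already an event. The participants missed are those with no transfusion before the window closes and at least one afterwards, by Week 52.

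**2. How large the gap could be.** Let r be the share of an arm stopping for rescue, and f the share of those whose first transfusion falls after the window. Stops for other reasons add a further term of the same form. Then:

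- understatement of the percentage in an arm = r × f
- distortion of the between-arm difference = (r₁ − r₂) × f, with f equal in both arms

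The documents give neither r nor f. The values below are assumptions chosen to show a range: f from 0.25 to 0.50, r from 2% to 10%.

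| r, one arm vs the other | f = 0.25 | f = 0.50 |
|---|---|---|
| 2% vs 2% | 0 points | 0 points |
| 5% vs 2% | 0.03 × 0.25 = 0.75 points | 0.03 × 0.50 = 1.5 points |
| 10% vs 5% | 0.05 × 0.25 = 1.25 points | 0.05 × 0.50 = 2.5 points |
| 10% vs 2% | 0.08 × 0.25 = 2.0 points | 0.08 × 0.50 = 4.0 points |

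In participants, using the planned arms of 268 (daprodustat) and 134 (epoetin alfa) and taking 5% vs 2% with daprodustat higher: 268 × 0.05 × 0.25 = 3.4 to 268 × 0.05 × 0.50 = 6.7 missed on daprodustat, and 134 × 0.02 × 0.25 = 0.7 to 134 × 0.02 × 0.50 = 1.3 on epoetin alfa. Swapping the arms reverses the sign of the distortion. Nothing in the documents says which arm, if either, will have more rescue.

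**The case against.** The case for leaving the plan alone is a fair one. The endpoint is exploratory, and the protocol (10.3.1) leaves exploratory methods to the analysis plan, so an on-treatment derivation is a delegated choice and its absence from SAP Table 1 is not a serious omission. The table titles say on-treatment openly. The principal secondary endpoint, IV iron, uses the same strategy as its main analysis. After a Step 2 stop, care follows local practice, so later transfusions partly reflect non-study therapy. Stopping for rescue is analysed separately as a secondary endpoint (SAP 7.3.1). All of this stands, and it is why replacing the on-treatment analysis would be a preference about the estimand and not a correction.

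A reader might infer three stronger things that the documents do not support:
- *Transfusions for treatment failure are left out as a class.* They are not. Step 1 transfusions for inadequate response are given on study treatment and counted, as are units given before a Step 2 stop.
- *The displays favour the less effective arm.* That needs first transfusion after stopping to differ by arm, and no rates are given. Step 1 also comes before Step 2, so an arm with more rescue might well show more on-treatment transfusions too.
- *The patient-year rates are wrong.* Numerator and person-time both end at treatment stop, apart from the extra day, so the rates are a broadly coherent while-on-treatment measure.

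The objection does not answer the percentage. Matching person-time cannot repair a proportion of all randomized participants described as by Week 52 but observed only to treatment stop. The separate rescue endpoint records stopping, not transfusion, and does not cover those who stop for other reasons and are transfused later.

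**Conclusion.** The concern holds for the percentage transfused by Week 52 and for time to first transfusion. The percentage is understated in each arm by the share of participants whose first transfusion comes after the window closes; it cannot be overstated by this rule. The time-to-first model censors at a stop that is likely to be informative when low hemoglobin caused it.

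The effect on the comparison between arms is unknown in both direction and size. It is nil if first transfusion after stopping is equally common in the two arms. The 0 to 4 points shown above rest wholly on assumed rescue and transfusion shares.

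The consequence is limited, because no multiplicity-controlled claim depends on this endpoint. The label is cheap improvement. The three inconsistent end-of-window rules need reconciling whatever view is taken of the estimand.

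**What to change.** 1. Keep the on-treatment displays, and label the existing percentage as on-treatment wherever it is now described only as by Week 52.
2. Add a supportive analysis of all transfusions from randomization to Week 52 regardless of treatment status, following the on- and off-treatment analysis already planned for IV iron in SAP 7.2.5.1. Include the percentage with at least one transfusion, the numbers of transfusions and units, and time to first transfusion. Take person-time to the earliest of Week 52, study withdrawal or death.
3. State one end of window for the on-treatment transfusion displays, and align SAP 14.4.1.1, the time-to-first period in 14.6.3.4 and the title of Figure 2.035 with it.

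The cost is SAP wording and a few extra displays for an exploratory endpoint, from data already collected. The added results would need a note that transfusions after stopping partly reflect non-study therapy.

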**CONFIDENTIAL**

204837

- For records with a frequency of “PRN”, the number of transfusions for each record will be equal to the number of units recorded
- For other transfusion records, the number of transfusions will equal the duration (end date – start date +1) times a multiplier, as defined below. The number of transfusions should be rounded to nearest integer.

Frequency	Multiplier
QM	0.033
Every 2 weeks	0.071
Once a week	0.14
Q4D	0.25
2 times per week	0.29
Q3D	0.33
3 times per week	0.43
Every other day	0.5
4 times per week	0.57
5 times per week	0.71
BID	2
Q12H	2
TID	3
Q8H	3
QID	4
Q6H	4
5 times per day	5
Q4H	6

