**Iron Endpoints****Baseline Iron Use**

- The number and percentage of subjects in the following iron use categories at baseline will be summarized:
  - IV iron use only
  - Oral iron use only
  - Other iron use only
  - IV and oral iron use only
  - IV and other iron use only
  - Oral and other iron use only
  - IV, oral, and other iron use
  - No iron use
- When determining baseline iron use, the gap factors mentioned below in the IV iron standardization algorithm will be applied to the end date for each iron record, and the baseline period of 12 weeks before the Randomization date until the day before the Randomization date will also be used.

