**CONFIDENTIAL**

204837

end date, the dates of individual transfusions are unknown and the number of transfusion events will be set to missing/unknown.

- In the case of a sequence of more than two transfusions, transfusions are considered to be the same Transfusion Event if the gap between each transfusion and the first transfusion in the sequence (the “anchor” transfusion) is 5 days or less. The first transfusion that is greater than 5 days after the “anchor” transfusion is not included in the Transfusion Event, and it becomes the new “anchor” transfusion for a new Transfusion Event.
- In the example below, transfusion records 1 and 2 would be grouped into a single Transfusion Event, because the gap between the transfusions (17JAN2019 to 18JAN2019) was 5 days or less. Record 3 falls outside this Transfusion Event because the gap between the start date (22JAN2019) and the previous anchor date (16JAN2019) is more than 5 days. Therefore 22JAN2019 becomes the new “anchor” transfusion used to define the next Transfusion Event. This pattern is repeated, if necessary. N.B. “anchor” transfusions are shown in bold.

#	Dose	Frequency	Transfusion Dates		Comment
			Start Date	End Date	
1	1 unit	Once only	16JAN2019	16JAN2019	1 Transfusion Event
2	1 unit	Once only	19JAN2019	19JAN2019	
3	1 unit	Once only	22JAN2019	22JAN2019	1 Transfusion Event
4	1 unit	Once only	25JAN2019	25JAN2019	
5	1 unit	Once only	28JAN2019	28JAN2019	1 Transfusion Event

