### Number of Units

- The number of RBC and whole blood units are derived from blood transfusion records. The number of units associated with each record is determined by the frequency, start date, end date and dose (i.e. number of units recorded), as described below.
- Only units associated with on-treatment transfusions are included. “End date” below refers to the end date defined for the transfusion, or the end of the on-treatment period, if sooner (see Section [14.4.1.1](#)).
- For records with the frequency recorded as “Once only” or “Continuous infusion”, the total number of units associated with each record is the number of units recorded (regardless of start and end dates)
- For records with the frequency recorded as “Once daily”, the total number of units associated with each record will equal the number of units recorded multiplied by the duration (end date – start date +1)
- For records with the frequency recorded as “PRN”, the total number of units will be equal to the number of units recorded (regardless of start and end dates)
- For other records, the number of units will equal to the number of units recorded multiplied by the duration (end date – start date +1) times a multiplier, as defined for Number of RBC and Whole Blood Transfusions above
- The table below provides multipliers for converting various reported units to Units (which should be rounded to nearest integer). For example, a transfusion of 450ml represents a single unit:  
 $(450 \times 0.0025) = 1.125$  (rounded to 1 Unit)

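### If the end date is the last transfusion, records coded monthly to three times per week omit the last interval: a lone transfusion counts as 0 and a series is usually one short

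*SAP*

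**What the plan says.** SAP 14.6.3.4 (Number of RBC and Whole Blood Transfusions) sorts records by frequency code. Once only and Continuous infusion records count as one transfusion. Once daily records count as the number of days. PRN records count as the number of units recorded. The rest use a formula: "For other transfusion records, the number of transfusions will equal the duration (end date – start date +1) times a multiplier, as defined below". The table that follows has 18 codes, with entries such as "Once a week 0.14", and "The number of transfusions should be rounded to nearest integer". The end date is replaced by the end of the on-treatment period if that comes sooner.

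The Number of Units subsection uses the same product: "For other records, the number of units will equal to the number of units recorded multiplied by the duration", times the same multiplier. It converts millilitres at 0.0025 per mL with rounding to the nearest unit, but rounds up non-integer units entered on the eCRF.

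The iron algorithms in SAP 14.6.3.2 treat record end dates differently: "the gap factors mentioned below in the IV iron standardization algorithm will be applied to the end date for each iron record". The IV iron dose derivations and the prior-ESA derivation in 14.6.2.1 do the same (6 days for weekly, 13 for every 2 weeks, 2.5 for twice weekly and so on). The transfusion rules have no gap factor.

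**The concern.** A course with equal intervals, whose first and last transfusions fall on the start and end dates, contains one more transfusion than it has intervals. Multiplying the inclusive days by the daily frequency gives credit for only one day of the final interval. For codes with long intervals, rounding to the nearest integer then removes the last transfusion, and a record with a single transfusion falls to zero.

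The participants affected are those who were transfused, some repeatedly. The SAP would also disagree with itself. Time to first transfusion uses the record's start date, so a participant could have an event there and contribute zero to transfusions per 100 patient-years.

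**Working it through.** **Plan's own figures.** The worked conversion reproduces: 450 x 0.0025 = 1.125, rounded to 1 unit. The less-than-daily multipliers also reproduce as frequency per day (1/30.4375 = 0.033, 1/14 = 0.071, 1/7 = 0.14, 2/7 = 0.29, 3/7 = 0.43, 4/7 = 0.57, 5/7 = 0.71). The SAP gives no worked example for a repeat-frequency record.

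**Formulas.** As written: count = round[(end − start + 1) x multiplier]. With a gap factor: count = round[(end − start + 1 + gap) x multiplier]. Assumptions: the end date is the date of the last transfusion, halves round up, and monthly means 30 days apart. The gap is the IV iron value, or the interval minus 1 day where the iron table has no entry (Q4D, Q3D, every other day).

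| Code (multiplier; gap in days) | One transfusion, as written | Two transfusions, as written | One, with gap | Two, with gap |
|---|---|---|---|---|
| Monthly (0.033; 29) | 0.033 → 0 | 31 x 0.033 = 1.02 → 1 | 0.99 → 1 | 1.98 → 2 |
| Every 2 weeks (0.071; 13) | 0.071 → 0 | 15 x 0.071 = 1.07 → 1 | 0.99 → 1 | 1.99 → 2 |
| Weekly (0.14; 6) | 0.14 → 0 | 8 x 0.14 = 1.12 → 1 | 0.98 → 1 | 1.96 → 2 |
| Q4D (0.25; 3) | 0.25 → 0 | 5 x 0.25 = 1.25 → 1 | 1.00 → 1 | 2.00 → 2 |
| Twice weekly (0.29; 2.5) | 0.29 → 0 | 4 or 5 days: 1.16 or 1.45 → 1 | 1.02 → 1 | 1.89 or 2.18 → 2 |
| Q3D (0.33; 2) | 0.33 → 0 | 4 x 0.33 = 1.32 → 1 | 0.99 → 1 | 1.98 → 2 |
| Three times weekly (0.43; 1.33) | 0.43 → 0 | 3 days: 1.29 → 1; 4 days: 1.72 → 2 | 1.00 → 1 | 1.86 or 2.29 → 2 |

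**Longer series.** For 2 to 8 true transfusions, the share of patterns that come out one short is 7/7 for each of monthly, every 2 weeks, weekly, Q4D and Q3D. It is 24/28 for twice weekly (days 0 and 3 or 0 and 4) and 14/21 for three times weekly (days 0, 2, 4), using every starting position. With the gap factor, all of these are exact.

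**Codes that behave differently.** Every other day loses none of 7 if halves round up, but the SAP does not state the tie rule and a one-day record gives exactly 0.5. Four times weekly loses one in 36 of 84 patterns. Five times weekly loses one in 17 of 35 and sometimes gains one. The eight sub-daily codes lose nothing (a one-day BID record gives 1 x 2 = 2).

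**Units.** Two units at each of two weekly transfusions give 2 x 8 x 0.14 = 2.24, against 4 units given. The SAP does not clearly say that this product is rounded, so a one-unit, one-day weekly record gives 0.14 unit. For volumes, 199 x 0.0025 = 0.4975, which rounds to 0 units.

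**The case against.** The strongest objection is that 14.6.3.4 never says the end date is the last transfusion. If sites enter the end of the interval covered, the formula is right: a weekly record of 7 days gives 7 x 0.14 = 0.98, counted as 1. The opposite reading rests on inference. SAP 14.4.1.5 assumes a medication was taken on its stop date, but it is written for concomitant medication. The iron and ESA gap factors make sense only if a record's end date is the last administration, but the SAP does not give their purpose. The Once daily rule fits both readings. I think the inference is sound, but it should be stated as an assumption.

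Part of the problem survives on either reading, because the end date is cut at the end of the on-treatment period. A weekly record cut to 3 days gives 0.42, an every-2-weeks record cut to 7 days gives 0.497, and a monthly record cut to 15 days gives 0.495. Each counts as 0 although the transfusion on the start date was on treatment.

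A second objection is that a one-day record coded weekly contradicts itself, and the SAP's single-day examples are all coded Once only. That is fair, and nothing in the documents shows that such records occur. But a series of two or more needs no odd coding to lose one, and the SAP lists these codes because it expects to meet them.

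A reader might also take the PRN rule as an error, since for records with unequal dates "the dates of individual transfusions are unknown and the number of transfusion events will be set to missing/unknown". The documents do not support that. It is an explicit, prespecified choice where dates are unknown, and these records still contribute transfusions and units.

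**Conclusion.** The rule is wrong as written for seven of the 18 multiplier codes: monthly, every 2 weeks, weekly, Q4D, Q3D, twice weekly and three times weekly. Given that the end date is the last transfusion, a lone transfusion counts as 0 and a series usually loses one. Units are understated through the same product, and converted volumes under 200 mL become 0 units.

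A reader might infer that most repeat-frequency records lose a transfusion. The arithmetic does not show that. The other 11 multiplier codes do not lose one in most patterns (every other day depends on the tie rule), and Once only, Continuous infusion, Once daily and PRN records do not use the multiplier. A reader might also infer that the need-for-transfusion results as a whole are undercounted. They are not: transfusion events come from grouping records and time to first transfusion from start dates. The effect is confined to transfusions and units per 100 patient-years, which SAP 7.4.1 places among the exploratory endpoints. No primary, principal secondary or secondary result changes. The total effect cannot be sized, because the mix of frequency codes is not in the documents, and there is no basis for claiming a bias between arms.

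**What to change.** In SAP 14.6.3.4, for the less-than-daily codes only:

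- Define the end date as the date of the last transfusion.
- Add to it the gap factor already used for IV iron (interval minus 1 day for Q4D, Q3D and every other day), then cap the result at the end of the on-treatment period.
- Set a minimum of one transfusion per on-treatment record, and state the tie rule.
- Compute units as this count times the units per transfusion. Keep nearest-integer conversion of volumes, with a minimum of 1 unit.

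Adding 1 to the rounded interval count looks simpler but is worse. A weekly record cut at day 6 would give round(6 x 0.14 = 0.84) + 1 = 2 for one transfusion, and a one-day BID record would fall from 2 to 1 if the rule reached sub-daily codes. Rounding volumes up would contradict the SAP's example by making 450 mL two units.

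Two small limits remain. For five times weekly the 0.4-day gap factor is exact in only 17 of 35 patterns. A record that runs up to the end of treatment can still be one short because of the cap (weekly transfusions on days 0 and 7 with the period ending on day 7: 8 x 0.14 = 1.12, counted as 1).

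The cost is a few lines of SAP text and a short change to one derivation, best made before unblinding. No new data are needed.
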